10. SAFETY

10.1 Drug studies

Not applicable.

10.2 Medical Device Category C studies

Not applicable.

10.3 Medical Device Category A studies

Not applicable.

10.4 Other clinical studies Category A

10.4.1 Serious adverse events

A serious adverse event is defined as any adverse event where it cannot be excluded that the event is attributed to study, and which

- Requires inpatient treatment not envisaged in the protocol or extends a current hospital stay;
- results in permanent or significant incapacity or disability; or
- is life-threatening or results in death.

The Sponsor Investigator is immediately notified (within 24 hours) if urgent safety and protective measures have to be taken during the conduct of the study. If a serious event occurs, the research project will be interrupted. The Ethics Committee will be notified via BASEC of these measures and of the circumstances necessitating them within 15 days.

10.4.2 Adverse events

We will document all adverse events following the vaporization of the e-Liquids until end of visit 2 assessing causality and severity.

11. STATISTICAL METHODS

A within-subject design is performed to achieve more Power than a between-subject design by partitioning between-subject variance out of the error variance. No carryover-effects (e.g. practice, fatigue) are expected.

A significance level of $p < 0.05$ (two-sided) will be considered as significant. As there is only one primary outcome measure, no Bonferroni correction will be applied.

11.1 Hypothesis

Cannabidiol has an influence on episodic memory.

11.2 Determination of Sample Size

We are interested to detect cannabinol effects with at least medium effect sizes. The estimation of $N=34$ is based on a power analysis using dependent t-tests assuming to detect a medium effect size ($d_z = 0.5$) with a power of 80% at $\alpha = 0.05$ (software: G-power 3).

11.3 Statistical criteria of termination of trial

The study will be terminated, as soon as 34 participants will have completed the entire study.

11.4 Planned Analyses

All analyses will be done in R. Episodic memory performance (memory free recall) and secondary variables of interest will be analyzed by calculating linear mixed models with subject as random effect, experimental condition (Cannabidiol versus placebo) as contrast of interest (fixed effect) as well as the interaction term between experimental condition and covariates (sex, age). In case of significant interactions between covariates and experimental condition, post-hoc tests will be applied to describe the interaction.

Furthermore, to control for possible confounders, possible confounders (words immediate recall, MADRS-S, sociodemographic variables, VAS for mood / arousal / motivation / tiredness / headache / tolerance), subjects' believe about group allocation, will be entered into the model as covariates (each covariate entering the statistical analyses separately).

In case of no significant influence of covariates on dependent variables and in case of no significant interaction of covariate and experimental condition, we will consider to remove covariates out of the statistical model in order to reduce model complexity as far as possible (calculate t-tests in the simplest case).

To illustrate the influence on episodic memory change between experimental conditions, the delta values will be calculated and used dependent variable in an additional analyses. The delta values correspond to the difference in task performance between experimental conditions.

For interim analyses refer to 11.4.3.

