ISO	International Organisation for Standardisation
ITT	Intention to treat
MADRS-S	Montgomery-Asperg Depression Self-rating Scale
MD	Medical Device
MedDO	Medical Device Ordinance (in German: MepV, in French: ODim)
NA	Not applicable
NG/ML	Nanogram per millilitre
PI	Principal Investigator
SD	Source Data
SDV	Source Data Verification
SOP	Standard Operating Procedure
SPC	Summary of product characteristics
SUSAR	Suspected Unexpected Serious Adverse Reaction
THC	Delta-9-tetrahydrocannabinol
TMF	Trial Master File

STUDY SCHEDULE

Procedure	Visit	Duration (min)	Starting time Visit 1 1 day (+ 3 month) after Tel. Screening	Starting time Visit 2 2 week (+ 8 week) after Visit 1
Telephonescreening				
Inclusion / Exclusion criteria		10	-	-
Screening				
Informed consent	Visit 1	10	00:10	-
MADRS-S		5	00:20	-
Sociodemographic questionnaire		2	00:25	-
Mental - Health questionnaire		5	00:27	-
Concomitant medication		2	00:32	-
Inclusion / Exclusion criteria		1	00:34	-
Test battery 1, 2				
Urine sample	Visit 1, Visit 2 (cross-over)	8	00:35	00:00
AE / Medication Log		1	00:43	00:08
Primary Endpoint: Words learning and immediate recall		2	00:44	00:09
Vape		15	00:46	00:11
Secondary Endpoint: n-back		15	01:01	00:26
VAS of mood, arousal Confounding factors: VAS of motivation, tiredness, headache, tolerance		1	01:16	00:41
Primary Endpoint: Words short delay recall		3	01:17	00:42
Overall time			80min	45min
End Visit 1 and Visit 2				

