6. STUDY DESIGN

6.1 General study design and justification of design

This is a single center clinical study comparing effects of CBD e-liquid versus a perfumed e-liquid on physiological processes (episodic memory) in healthy subjects using the following design

- Randomized
- Double-blind
- Placebo-controlled
- Cross-over design
- Approx. equal number of male and female subjects in each group

The duration of the study - from first participant in to last participant out - lasts approximately 6 months. The duration for a participant will be approximately 80 minutes for visit 1, and 45 min for visit 2. Dropouts will be replacement until data of total needed sample size is completed.

The wash-out period between the two testing days lasts 14 days (approximately 10 half-lives of CBD (Ujvary & Hanus, 2016)) to 56 days (due to flexible recruiting).

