7. STUDY POPULATION

7.1 Eligibility criteria

Participants fulfilling all of the following inclusion criteria are eligible for the study:

- Healthy
- Normotensive (BP between 90/60mmHg and 140/90mmHg)
- BMI between 18 and 30 kg/m²
- Male or female
- Aged between 18 and 30 years
- Native or fluent German-speaking
- Able and willing to give written informed consent as documented by signature and comply with the requirements of the study protocol
- Willing to donate urine sample to control for pre-Visit CBD/THC consume

The presence of any one of the following exclusion criteria will lead to exclusion of the participant, for example:

- Acute or chronic psychiatric disorder including drug or alcohol abuse
- Women who are pregnant or breast feeding
- Intention to become pregnant during the course of the study
- Smoking (> 5 cigarettes per day)
- Participation in one of our previous studies using the same verbal test in the past 2 years
- Participation in a study with CBD / THC within the 30 days preceding and during the present study
- Known hypersensitivity or allergy to propylene glycol
- Intake of CBD / THC within the 7 days preceding and during the present study in any application form
- Long-term systemic medication or topical steroids to treat an underlying disease within last 3 months
- Inability to follow the procedures of the study, e.g. due to language problems, psychological disorders, dementia, etc. of the participant
- Enrolment of the investigator, his/her family members, employees and other dependent persons

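### The cross-over models have no visit (period) term, so with balanced sequences any visit shift goes into the error and makes the test conservative

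*Combined protocol and SAP*

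**What the plan says.** Section 11.4 analyses delayed recall and the secondary variables with "linear mixed models with subject as random effect, experimental condition (Cannabidiol versus placebo) as contrast of interest (fixed effect", together with condition-by-sex and condition-by-age interactions. Possible confounders (immediate recall, MADRS-S, sociodemographic variables, the VAS scores, belief about allocation) are added with "each covariate entering the statistical analyses separately". Covariates without a significant influence or interaction may be dropped, down to the point where the team would "calculate t-tests in the simplest case". Section 11.4.3 treats the secondary outcomes in the same way. Neither section, nor the statistics entry in the synopsis, names visit, period, order or sequence.

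The only related statement is in section 11: "No carryover-effects (e.g. practice, fatigue) are expected". Section 6.1 relies on the interval between visits: "The wash-out period between the two testing days lasts 14 days", extending up to 56 days. Section 6.2.1 randomises sequence in blocks, with separate lists for men and women. Section 9.3.1 (cognitive testing) provides parallel versions of the tests at the two visits, without saying how versions are assigned to visits.

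**The concern.** In a two-visit cross-over, anything that makes visit 2 differ from visit 1 for everyone adds to the paired difference in one sequence and subtracts from it in the other. Without a visit term this systematic spread is counted as random error. Practice and fatigue work in this way whichever product came first. They are period effects, so a wash-out chosen from the half-life of CBD does not deal with them.

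The documents give reasons to allow for such a shift:

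- **Different run-in.** In the Study Schedule, "Primary Endpoint: Words learning and immediate recall" starts at 00:44 at visit 1, after consent and questionnaires, and at 00:09 at visit 2.
- **Earlier exposure.** Section 7.1 excludes people for "Participation in one of our previous studies using the same verbal test in the past 2 years", yet every participant meets a parallel version of that task 14 to 56 days before visit 2.
- **Version assignment.** If versions are used in a fixed order, any difference in difficulty between them is itself a visit shift.

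What is at stake is sensitivity. A real effect becomes easier to miss in a trial whose calculated power exceeds its target by less than one point. The n-back is the most exposed outcome: in the schedule "Secondary Endpoint: n-back" comes only after vaping, so no pre-vape score of that task exists to absorb a shift. The VAS scores are also taken after vaping.

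**Working it through.** **Inputs from the documents.** Two-sided alpha 0.05 (section 11); dz = 0.5, 80% power, dependent t-test, N = 34 (section 11.2); balanced blocks (section 6.2.1), taken as 17:17. The size of the visit shift is not given. It is an assumption here, varied from 0 to 1.0 SD of the paired difference.

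**Step 1: the plan's own figure.** Power of the paired t-test comes from the noncentral t with noncentrality dz × √N.

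- N = 34: 0.5 × √34 = 2.915, df 33, power 80.8%.
- N = 33: power 79.5%.

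So 34 is the smallest adequate N, and the sample size is reproduced.

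**Step 2: cost of the visit term when there is no shift.** The noncentrality is unchanged and df falls from 33 to 32. Power goes from 80.8% to 80.7%.

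**Step 3: leaving the term out (reading A).** Let the paired difference (CBD minus placebo) be δ ± s + e, with the sign set by sequence and SD(e) = 1. With 17:17 the mean difference still estimates δ without bias. The sum of squares in the paired t-test, however, follows a noncentral chi-square with 33 df and noncentrality 34 × s². Reading A takes dz = 0.5 relative to SD(e). Integrating over that distribution gives:

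| Shift s (SD) | Power without term | Type I error without term | Power with term |
|---|---|---|---|
| 0 | 80.8% | 5.0% | 80.7% |
| 0.10 | 80.5% | 4.9% | 80.7% |
| 0.15 | 80.1% | 4.8% | 80.7% |
| 0.25 | 79.0% | 4.4% | 80.7% |
| 0.50 | 73.5% | 2.9% | 80.7% |
| 0.75 | 64.1% | 1.5% | 80.7% |
| 1.00 | 51.3% | 0.6% | 80.7% |

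Power crosses 80% near s = 0.17. At s = 0.5 the interval is wider by about √(1 + 0.25 × 34/33) = 1.12, that is 12%. Regaining 80% power there without the term would take about 42 participants. With the term, type I error is 5% throughout. Simulation agrees with these figures.

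**Step 4: reading B.** Suppose dz = 0.5 refers to raw paired differences that already contain the visit variance. Then the residual SD is √(1 − s²).

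- s = 0.25: residual SD 0.968, so the effect is 0.516 residual SD. Power is 81.5% without the term and 83.1% with it.
- s = 0.50: residual SD 0.866, effect 0.577. Power is 83.8% without (type I error 2.4%) and 90.4% with it.

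**Step 5: does immediate recall already do the job?** Reading A, s = 0.5, immediate recall kept as covariate; the correlation of the paired differences is assumed (simulation):

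| Correlation | Where the shift falls | Power without term | Power with term |
|---|---|---|---|
| 0.5 | both recall scores | 88.2% | 89.5% |
| 0.5 | delayed recall only | 82.6% | 89.6% |
| 0.3 | both recall scores | 80.3% | 83.2% |
| 0.3 | delayed recall only | 75.4% | 83.1% |

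The covariate absorbs much of a shared shift, but not one that arises after learning.

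**Step 6: imbalance.** The bias without the term is s × (n1 − n2)/N. For 18:16 and s = 0.5 it is 0.5 × 2/34 = 0.03 SD. Simulated type I error at s = 0.5 is 3.1% at 18:16, about 5% at 20:14, and 9.0% at 22:12, where the bias is 0.5 × 10/34 = 0.15 SD.

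**The case against.** The strongest reply is that nothing invalid results. With balanced sequences the estimate is unbiased and the test errs on the safe side. Section 11.2 states dz for a dependent t-test, so reading B is the natural one, and under it the plan meets its 80% target without the term. The large losses need shifts equal to or twice the targeted effect, and no passage supports a shift of that size. All of this stands. It makes the term an efficiency gain under reading B and keeps the point from being a fatal flaw.

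The evidence for a shift can also be read more mildly. The listed screening steps add up to 25 minutes (10 + 5 + 2 + 5 + 2 + 1); 35 minutes is the difference in clock time between the visits. The two-year exclusion may be aimed at memory for the same words, which parallel versions address. Constant time of day and standardised testing (section 6.2.3) help too, and the interval from learning to recall is 33 minutes at both visits (00:44 to 01:17 and 00:09 to 00:42). These points weaken the expectation of a shift but do not rule one out.

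For the primary outcome, immediate recall is likely to predict delayed recall and so to be retained. That is a real mitigation, but a partial one: it enters separately, may be removed, misses shifts that arise after learning, and has no counterpart for the n-back.

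Finally, the conservative direction depends on near balance. Section 11.4.1 allows outliers to be removed without a stated rule, and marked imbalance (beyond about 20:14) would turn the error the other way. Blocking, and replacement of drop-outs in list order (section 7.4), make that unlikely.

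**Conclusion.** The concern holds. The primary model, the secondary models and the t-test fallback all omit visit, and the expectation stated in section 11 does not justify this, because it treats period effects as carry-over. Under the planned balance the consequence is lost precision and a conservative test, with no bias. The amount depends on a shift the documents do not quantify: under one point of power up to about 0.15 SD, about 2 points at 0.25 SD and about 7 points at 0.5 SD under reading A. Under reading B the 80% target is met, but at 0.5 SD about 6.6 points of available power are given up (90.4 − 83.8). Against this, including the term costs about 0.1 point when there is no shift. The change should be made. It must be fixed in advance, because section 11.4 lets terms be dropped on significance and a visit term added after seeing the data would be a discretionary choice.

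**What to change.** - Add visit (1 or 2) as a fixed effect in the primary and secondary mixed models in section 11.4, and exempt it from the covariate-removal rule so that it stays regardless of significance.
- Replace the plain t-test fallback with the period-adjusted cross-over contrast (the treatment difference adjusted for sequence). Apply the same adjustment wherever the delta values are tested.
- Reword section 11 so that practice and fatigue are named as period effects handled by the visit term, separately from pharmacological carry-over.
- State how parallel versions are assigned. If they are tied to visit, the visit term covers them. If not, balance them within sequence and add a version term.

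The visit term costs one error degree of freedom (80.8% to 80.7% power with no shift); a version term, if needed, costs a little more. No new data are required, and N=34 can stay.

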Control Intervention (if applicable):	Single vape of 0.25ml e-liquid La Baronne Jaune, BORDO2 tastes like lemon and madeleine. 15min vape time.
Number of Participants with Rationale:	We are interested to detect cannabidiol effects with at least medium effect sizes. The estimation of N=34 is based on a power analysis using dependent t-tests assuming to detect a medium effect size ($d_z = 0.5$) with a power of 80% at $\alpha = 0.05$ (software: G-power 3).
Study Duration:	Study duration is estimated 6 months
Study Schedule:	First participant in 10/2018 (planned) Last participant out 03/2019 (planned)
Investigator(s):	
Sponsor-Investigator [name] [name], MD Division of Cognitive Neuroscience University of Basel [name] [contact] [contact] Email: [contact]
 
Subinvestigator [name] Division of Cognitive Neuroscience University of Basel [name] [contact] [contact] Email: [contact]

Study Centre(s):	Division of Cognitive Neuroscience University of Basel
Statistical Considerations:	A significance level of $p < 0.05$ (two-sided) will be considered as significant. All analyses will be done in R. The differences between the experimental conditions will be analyzed using linear mixed models in combination with analysis of variance (SS II).

GCP Statement:	This study will be conducted in compliance with the protocol, the current version of the Declaration of Helsinki, the ICH-GCP or ISO EN 14155 (as far as applicable) as well as all national legal and regulatory requirements.
-----------------------	---

ABBREVIATIONS

AE	Adverse Event
BASEC	Business Administration System for Ethical Committees, (https://submissions.swissethics.ch/en/)
BMI	Body mass index
BP	Blood pressure
CA	Competent Authority (e.g. Swissmedic)
CB1 receptors	Cannabinoid 1 receptors
CB2 receptors	Cannabinoid 2 receptors
CBD	Cannabidiol
CEC	Competent Ethics Committee
CRF	Case Report Form
ClinO	Ordinance on Clinical Trials in Human Research (in German: KlinV, in French: OClin, in Italian: OSRUm)
eCRF	Electronic Case Report Form
CTCAE	Common terminology criteria for adverse events
DSUR	Development safety update report
EKNZ	Ethikkommission Nordwestschweiz
GCP	Good Clinical Practice
IB	Investigator's Brochure
Ho	Null hypothesis
H1	Alternative hypothesis
HRA	Federal Act on Research involving Human Beings (in German: HFG, in French: LRH, in Italian: LRUm)
IMP	Investigational Medicinal Product
IIT	Investigator-initiated Trial

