11.4.2 Primary Analysis

Primary outcome analyses will be performed after completed data sampling (see 11.3, 11.4) by study statistician.

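### Section 11.4 plans to adjust free recall for six VAS ratings taken only after vaping, and no section names the primary model

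*Combined protocol and SAP*

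**What the plan says.** **Base model.** The first paragraph of 11.4 gives a linear mixed model with subject as random effect and "experimental condition (Cannabidiol versus placebo) as contrast of interest (fixed effect", plus interactions of condition with sex and age.

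**Covariates.** The second paragraph adds possible confounders: immediate recall, MADRS-S, sociodemographic variables and "VAS for mood / arousal / motivation / tiredness / headache / tolerance". What participants think they received is treated likewise: "believe about group allocation, will be entered into the model as covariates". The manner of entry is given as "each covariate entering the statistical analyses separately".

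**Removal.** The third paragraph first sets a condition: "In case of no significant influence of covariates on dependent variables and in case of no significant interaction of covariate and experimental condition". When that condition is met, the plan undertakes only the following: "we will consider to remove covariates out of the statistical model in order to reduce model complexity as far as possible". The simplest case it allows is a t-test.

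**Primary analysis.** Section 11.4.2 reads in full: "Primary outcome analyses will be performed after completed data sampling (see 11.3, 11.4) by study statistician". It gives timing and analyst, and names no model. In 11.4 only the delta-value analysis is called additional.

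**Timing.** The Study Schedule and section 9.3.1 (cognitive testing) place the VAS once per visit, after vaping and the n-back and just before delayed recall. No VAS before vaping is scheduled. Allocation belief has no row in the schedule, and its time of collection is not stated.

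**The concern.** A confounder of condition must influence, or share a cause with, the condition received. Section 6.2.1 randomises the order of conditions, so a rating taken after vaping cannot play that part. It can lie on the path from CBD to recall. The protocol itself names somnolence as a risk (3.7) and headache as a side effect (4.4), and lists mood and arousal as outcomes of interest (5.3). Section 5.3 and the schedule call only four of the VAS confounders; 11.4 treats all six that way.

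The primary objective (4.2) is the effect of CBD on episodic memory, which is a total effect. If CBD shifts a rating related to recall, conditioning on that rating removes or adds part of the effect. The adjusted contrast can then be too small, too large, or non-zero when there is no total effect. The removal rule is no safeguard: removal is discretionary, and it is considered only for covariates without a significant effect or interaction. A rating that predicts recall does not meet that condition. With no model labelled primary, the choice between adjusted and unadjusted contrast can be made after the data are seen.

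**Working it through.** **1. Timing (Study Schedule).** Visit 1: vape 00:46, VAS 01:16, delayed recall 01:17. Visit 2: 00:11, 00:41, 00:42. The gap from start of vaping to VAS is 30 minutes at both visits.

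**2. The plan's own figure (11.2).** Paired t-test, dz = 0.5, two-sided 0.05. Power comes from the noncentral t with n - 1 df and noncentrality dz × √n = 0.5 × √34 = 2.92. This gives 80.8% at n = 34, so N = 34 is reproduced. The calculation contains no covariate.

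**3. Effect of adjusting for one VAS, paired-difference form.** Let d be the CBD minus placebo difference in recall and x the same difference in one VAS, each with SD 1. Let δ be the true total effect, s the shift of the VAS by CBD, and r the correlation of d and x. In the regression of d on x, the condition effect is the intercept:

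- estimate = δ - r × s
- SE ≈ √(1 - r²) × √((1 + s²)/n), tested on n - 2 = 32 df

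The documents give neither s nor r; all values below are assumptions. With δ = -0.5 and n = 34:

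- s = 0, r = -0.4: estimate -0.50; SE ≈ 0.917 × √(1/34) = 0.157.
- s = 0.2, r = -0.2: estimate -0.5 + 0.04 = -0.46; SE ≈ 0.980 × √(1.04/34) = 0.171.
- s = 0.5, r = -0.3: estimate -0.5 + 0.15 = -0.35; SE ≈ 0.954 × √(1.25/34) = 0.183. With δ = 0 the estimate is +0.15.

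**4. Mixed-model form.** Simulation of a random-intercept model with condition, sex, age, their interactions with condition, and one VAS. Person-level variance is 1 and the person-level VAS-recall correlation is 0. It was run with the VAS always in, and with the VAS kept only if its main effect or interaction has p < 0.05. The second version is one reading of 11.4 and treats removal, which the plan will only consider, as automatic.

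Simulated results (estimate; power; rejection when δ = 0):

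| Assumed s, r | Paired difference, always adjusted | Mixed model, always adjusted | Mixed model, VAS kept if significant |
|---|---|---|---|
| 0, -0.4 | -0.50; 86%; 5% | -0.50; 85%; 5% | -0.50; 84%; 5% |
| 0.2, -0.2 | -0.46; 73%; 6% | -0.48; 76%; 5% | -0.49; 79%; 5% |
| 0.5, -0.3 | -0.35; 45%; 12% | -0.41; 60-61%; 8% | -0.45; 70-71%; 8% |

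Unadjusted, each row gives -0.50, about 81% and 5%. The forms differ because the random-intercept model pools within-person and between-person association, which dilutes the slope when the person-level correlation is 0. Varying that correlation from -0.4 to +0.4 moves the last cell from -0.35 to -0.50, power from 49 to 79% and null rejection from 15 to 6%.

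**5. Direction.** With s = 0.5 and r = +0.3 the paired-difference estimate is -0.5 - 0.15 = -0.65, so the effect is overstated. The mixed model gives -0.59 always adjusted and -0.55 with the VAS kept if significant.

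Several VAS entered together, and allocation belief, were not simulated.

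**The case against.** **The benign reading.** The first paragraph of 11.4 reads as the main model. The next paragraph adds covariates one at a time, as a set of checks would. The synopsis names mixed models with Type II analysis of variance and no covariate, and the sample size rests on a paired t-test. A reader might infer that the primary result will be VAS-adjusted and therefore biased. The documents do not support that inference: they plan the adjustment but do not say it supplies the main result. Nor do they state that a significant VAS replaces the base model; that is an inference from the removal rule. What stands is that the adjustment is firmly planned, is justified as control of confounding, and is not labelled a sensitivity analysis.

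**Selection among models.** A reader might also infer that the smallest p-value from seven models (unadjusted plus six VAS) will be reported. In simulation that gives 7.9 to 13.7% error even with no VAS shift (r from 0 to 0.5). This is a worst case; nothing in the plan says the best result will be chosen.

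**Small shifts.** Section 8.2.1 calls the dose low, and section 3.5 puts it below the 16 to 600 mg of the studies described. Marked harm needs a VAS shift of about 0.5 SD, the size the trial targets for memory itself. This stands, and it limits the weight of the point.

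**Precision.** If CBD leaves a predictive VAS unchanged, adjusting for it is unbiased and gains power. This also stands and is counted as a cost under the fix.

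**Conclusion.** The point holds as a fault of method and labelling. Ratings taken after vaping cannot confound a randomised condition, the plan enters them as confounders, and no model is named primary. It is not established that the primary result would be VAS-adjusted.

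The size is unknown. For one VAS, under the assumptions above:

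- Shift 0: no bias.
- Shift 0.2, r = -0.2: 81 - 79 = 2 to 81 - 73 = 8 points of power lost.
- Shift 0.5, r = -0.3: estimate -0.35 to -0.45 instead of -0.50, power 45 to 71% instead of 81%, null rejection 8 to 12%, depending on model form (person-level correlation 0 in the mixed model).

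Confidence is high on the text and the principle, and moderate on the consequence. The point should be fixed because the remedy is cheap. Allocation belief is a related gap in the wording and adds nothing to these figures.

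**What to change.** State one exact primary model in 11.4 and cite it in 11.4.2. For example:

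> The primary test is the condition contrast (CBD versus placebo, two-sided 0.05) for delayed free recall in a linear mixed model with subject as random effect and fixed effects for condition and visit-specific immediate recall (measured before vaping). No other covariate is added to or removed from this model on the basis of results. Condition-by-sex and condition-by-age terms are tested in separate secondary models. No variable measured after vaping starts enters the primary model.

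Report the six VAS as outcomes by condition. Label VAS-adjusted and belief-adjusted recall models exploratory, and state when allocation belief is collected. The covariate set must be closed: wording that merely permits pre-vaping variables would leave several primary models open after the data are seen.

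**Cost.** Wording only, with no new data and no change to visits. If CBD does not shift a VAS that predicts recall, some power is given up: 81% unadjusted against about 86% at |r| = 0.4 and about 89% at |r| = 0.5 (r assumed, paired-difference form). VAS-adjusted results become exploratory, and the sex and age interactions move to secondary models.
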